## **1.0 Study Hypotheses and Objectives**

### **1.1 Hypotheses**

1.1.1 Compared to continued ART, switch to bictegravir + tenofovir alafenamide + emtricitabine will not be associated with an adverse side effect profile and will maintain virologic control in HIV-infected transwomen (TW).

1.1.2 After 48 weeks, switch to bictegravir + tenofovir alafenamide + emtricitabine will be associated with improvements in circulating inflammatory and metabolic biomarker profiles (including mortality-associated biomarkers), bone mineral density, fat and lean mass quantities, hepatic fat and insulin resistance vs continued ART.

### **1.2 Primary Objective**

To determine the safety of bictegravir + tenofovir alafenamide + emtricitabine in HIV-infected TW.

### **1.3 Secondary Objectives**

1.3.1 To compare total, appendicular and trunk fat mass by DXA at 48 weeks between TW who switch to bictegravir + tenofovir alafenamide + emtricitabine compared to TW who remain on current ART.

1.3.2 To compare total and appendicular lean mass by DXA at 48 weeks between TW who switch to bictegravir + tenofovir alafenamide + emtricitabine compared to TW who remain on current ART.

1.3.3 To compare bone mineral density by DXA at 48 weeks between TW who switch to bictegravir + tenofovir alafenamide + emtricitabine compared to TW who remain on current ART.

1.3.4 To compare hepatic fat content, as measured by FibroScan controlled attenuation parameter (CAP) measurement, at 48 weeks between TW who switch to bictegravir + tenofovir alafenamide + emtricitabine compared to TW who remain on current ART.

1.3.5 To compare hepatic fibrosis, as measured by FibroScan liver stiffness measurement (LSM), at 48 weeks between TW who switch to bictegravir + tenofovir alafenamide + emtricitabine compared to TW who remain on current ART.

1.3.6 To compare frequency of insulin resistance, as measured by the homeostatic assessment model of insulin resistance (HOMA-IR), at 48 weeks between TW who switch to bictegravir + tenofovir alafenamide + emtricitabine compared to TW who remain on current ART.

1.3.7 To compare fasting lipid levels at 48 weeks between TW who switch to bictegravir + tenofovir alafenamide + emtricitabine compared to TW who remain on current ART.

1.3.8 To compare estimated GFR (using the CKD-Epi equation) at 48 weeks between TW who switch to bictegravir + tenofovir alafenamide + emtricitabine compared to TW who remain on current ART.

1.3.9 To compare AST and ALT levels at 48 weeks between TW who switch to bictegravir + tenofovir alafenamide + emtricitabine compared to TW who remain on current ART.

1.3.10 To compare differences in circulating inflammatory and metabolic biomarker levels (including mortality associated biomarkers) at 48 weeks between TW who switch to bictegravir + tenofovir alafenamide + emtricitabine compared to TW who remain on current ART.

## 2.0 Introduction

### 2.1 Rationale

#### Background

Hormone therapy for transgender persons is a critical component of both well-being and harmonizing gender identity and expression; however, female hormone therapy causes fat gain and modulates the body's inflammatory and coagulation pathways. Female hormone therapy has been associated with increased risk of cardiovascular and thromboembolic events (hereafter referred to in aggregate as cardiovascular disease, CVD) in natal females (persons assigned a female sex at birth) and TW, although little is known about metabolic disease of other organs in this population.

TW have an extremely high prevalence of HIV infection. A recent meta-analysis reported HIV prevalence rates up to 43.7% among TW, with an odds ratio (OR) for persons of reproductive age of 48.8 (95% Confidence Interval [CI] 21.2-76.3). The reasons underlying the epidemic level of HIV infection among TW are beyond the scope of this proposal, but the burden of HIV disease and its associated comorbidities must be considered in this vulnerable population.

[figure not shown]
Non-AIDS events are leading causes of morbidity and mortality among HIV-infected persons well controlled on antiretroviral therapy (ART), and these events may occur earlier in life or at increased frequency in the setting of HIV infection. Both female hormone therapy and ART are associated with fat gain and metabolic disturbances (Figure 1), and the intersection of HIV infection and female hormone therapy among TW may predispose to or exacerbate a number of metabolic diseases, including CVD, fatty liver disease, insulin resistance and osteoporosis. Similarly, the intersections of HIV-, ART- and female hormone therapy-induced alterations in immuno-metabolic pathways and subsequent metabolic disease risk in TW have not been studied, but could profoundly affect the health of this population.

#### Preliminary Data

Of 214 TW on hormone therapy (HIV status not reported), 10% experienced a thromboembolic event. TW experience significantly more myocardial infarctions than control women, cerebrovascular disease than control men, and diabetes mellitus than control women and men. Alarmingly, obesity, cerebrovascular disease and myocardial infarction rates dramatically increase with hormone initiation.

Active hormone therapy increases CVD death risk 3-fold. CVD risk appears highest with combined estrogen and progesterone or anti-androgen therapy vs estrogen alone, and is higher with oral vs transdermal estrogens. 17- $\alpha$ -ethinyl estradiol is associated with the greatest perturbations of inflammatory biomarkers, coagulation parameters and lipids, and is therefore no longer recommended as first-line hormone therapy for TW. However, no data exist on the incidence, prevalence or associations of modern female hormone therapy with fat or lean mass changes, bone health, liver disease or immuno-metabolic markers among TW, especially HIV-infected TW.

Visceral (including hepatic) fat gain with ART initiation is frequent and occurs with most modern ART regimens. The effects of female hormone therapy on metabolic disease prevalence in HIV-infected TW, however, are hard to predict, and data must currently be extrapolated from natal females and HIV-uninfected TW. For example, 40% of natal females initiating selective estrogen receptor modulators for breast cancer develop hepatic steatosis within 2 years, possibly from reduced fatty acid oxidation. Estrogen in natal females is associated with improved lipids, reduced fibrogenesis, preservation of mitochondrial function, anti-

**Figure 1. Contributions of HIV and hormone therapy to CVD.** Adapted from Hemkens and Bucher. Eur Heart J. 2014 Jun 1;35(21):1373-81.

oxidant effects that may be lost with menopause, and, with menopause-induced visceral fat gain, contributes to metabolic disease.

Supporting a relationship with metabolic disease, female hormone therapy increases subcutaneous and visceral adipose tissue, increases cortisol and triglyceride levels, and lowers lipoprotein lipase and insulin sensitivity. Oral estrogens increase IL-1, IL-6, IL-8, CRP and TNF- $\alpha$  levels. Additionally, access to appropriate hormone therapy is not widespread, and periods of ineffective androgen suppression and/or supra-physiologic estrogen levels from intermittent or unsupervised dosing may further metabolic and immunologic perturbations in TW.

### *Intervention*

Bictegravir (BIC, GS-9883) is a novel, potent, once-daily, unboosted HIV-1 integrase inhibitor. BIC displays a better *in vitro* resistance profile compared to the integrase strand transfer inhibitors raltegravir and elvitegravir, and is comparable to that of dolutegravir. BIC is being studied in Phase III trials with tenofovir alafenamide + emtricitabine as a once daily regimen for the treatment of HIV infection. In Phase II studies, BIC was well-tolerated, and no discontinuations of BIC for adverse events or clinically significant lab abnormalities occurred. Lipid and glucose levels, and assessments of lean mass, fat mass and bone mineral density with BIC have not yet been released, but would be expected to be similar or improved compared to other integrase inhibitors.

The integrase inhibitor class of agents may be the optimal ART base for TW, although no data exists in this population. However, given interactions between pharmacokinetic boosters and oral hormone therapy, regimens requiring low-dose ritonavir or cobicistat are likely suboptimal for TW on hormone therapy (excluding Stribild/Genvoya and most protease inhibitors). Similarly, due to increased CVD risk in this population, abacavir-containing regimens should likely be avoided (excluding Triumeq). While once daily dosing or single tablet regimens are preferred by most patients, they are especially important for patients with unstable housing and daily life schedules, which are frequent among TW (excluding traditionally-dosed raltegravir). This is also a population with high rates of food insecurity and depression (excluding Complera/Odefsey and Atripla as preferred options). Given these facts, once daily, unboosted bictegravir may be the ideal ART base for TW women. Additionally, female hormone therapy may have adverse effects on bone mineral density, and agents with improved bone health profiles, such as tenofovir alafenamide, will likely be beneficial in this population.

**There is currently no data on the efficacy or tolerability of bictegravir + tenofovir alafenamide + emtricitabine in HIV-infected TW.** Therefore, we propose a pilot, two-arm, randomized, open label study of current ART vs switch to bictegravir + tenofovir alafenamide + emtricitabine in HIV+ TW on hormone therapy and suppressive ART with two NRTIs plus a 3rd agent. The goal of this Phase IIb study is to evaluate the safety, tolerability and immuno-metabolic consequences of bictegravir + tenofovir alafenamide + emtricitabine in virologically suppressed, HIV-infected TW.

## **3.0 Study Design**

Participants will be randomized 1:1 to continue current ART or switch to bictegravir + tenofovir alafenamide + emtricitabine for 48 weeks. Blood collection for inflammatory and metabolic biomarker analysis will be performed at weeks 0, 24 and 48. DXA-quantified bone mineral density and lean and fat mass, and Fibroscan-quantified hepatic fat (CAP) and fibrosis (LSM) will be performed at weeks 0 and 48. DXA and Fibroscan will be performed locally at research rates. Blood will be collected on site and stored for batched inflammatory and metabolic biomarker processing.

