## **9.0 Sample Size and Endpoints**

### **9.1 Sample size**

Since a high percentage of participants are expected to have hepatic steatosis, we will base the sample size around the desired effect size for FibroScan CAP measurement. The sample size for this project is derived

from studies of CAP in HIV-infected but non-TW populations. Using a median baseline CAP of 237 dB/m (standard deviation [SD] 53), 20 TW per arm provides 90% power to detect a minimum between-group CAP difference of 56 dB/m, which is clinically significant. We will enroll 24 TW per arm to allow for up to 20% discontinuation or loss-to-follow-up, which is reasonable for this high-risk population. Therefore, the total sample size will be 48 participants.

Additionally, perturbations of inflammatory, metabolic and coagulation pathways by exogenous female hormone use and the intersections of these perturbations with those associated with HIV are unknown. Therefore, it should not be assumed that the effects of switching ART to bictegravir + emtricitabine + tenofovir alafenamide on immunometabolic biomarkers in transwomen will be similar to those observed with integrase inhibitor or tenofovir alafenamide use in other HIV-infected populations. As such, we will assess the effects of switching ART to bictegravir + emtricitabine + tenofovir alafenamide vs continued ART on multiple biomarkers, including soluble CD14 (sCD14), a monocyte activation and mortality-associated biomarker that has been previously been shown by us and others to decline following switch to an integrase inhibitor. If similar declines in sCD14 and variability are observed following switch to bictegravir + emtricitabine + tenofovir alafenamide, 48 participants will provide >99% power to observe this clinically significant effects.

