## **9.6 Analyses**

A descriptive analysis of demographic and clinical characteristics will be generated. Continuous variables will be expressed as mean  $\pm$  SD if normally distributed or median with IQR if not normally distributed. Data will be pooled by arm and stratified by ART 3rd drug class. CAP will be used continuously and categorically, using for the latter the following standardized steatosis cut-offs: Grade 1 238 dB/m, Grade 2 260 dB/m and Grade 3 292 dB/m. DXA data will be used continuously for lean and fat mass measurements, and, for bone mineral density, both continuously and categorically, with the latter using standard cutoffs for osteopenia and osteoporosis. Biomarker levels may be log-transformed, where appropriate. Wilcoxon rank-sum and Pearson  $\chi^2$  tests will compare continuous and categorical variables, respectively, between and within groups. Although the sample size is small, regression modeling will be attempted to assess if any observed differences persist after adjustment for confounding factors. All statistical tests will be 2-sided ( $\alpha=0.05$ ). Analysis will be exploratory without adjusting for multiple testing. [name] and [name] (statistician) will oversee analysis plan development/implementation.

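### Lipids, glucose, insulin and biomarkers are measured at Weeks 0, 24 and 48, but the planned comparison uses neither baseline nor Week 24, drops anyone without a Week 48 value, and has no rule for discontinuation-visit samples

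*Combined protocol and SAP*

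**What the plan says.** **Measurement.** Section 3.0: "Blood collection for inflammatory and metabolic biomarker analysis will be performed at weeks 0, 24 and 48". The schedule in Section 6.1 and the laboratory text in Section 6.6 give the same three times for fasting lipids, glucose and the samples banked for insulin. Safety laboratory tests (the source of eGFR, AST and ALT) have intermediate values at Weeks 4 and 12 only. FibroScan and DXA are done at Weeks 0 and 48.

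**Objectives.** Section 1.3 fixes the comparison at 48 weeks, for example in 1.3.10: "To compare differences in circulating inflammatory and metabolic biomarker levels (including mortality associated biomarkers) at 48 weeks". Objectives 1.3.6 (HOMA-IR) and 1.3.7 (lipids) use the same time point.

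**Analysis.** Section 9.6 says of the Wilcoxon rank-sum and Pearson chi-square that these "tests will compare continuous and categorical variables, respectively, between and within groups". It adds that regression will be attempted to adjust for confounders. It names no visit, no repeated-measures model, no role for Week 24 and no method for missing values. The exclusion rule in 9.6.1 is written for the primary endpoint, and the supplementary intent-to-treat analysis there has no missing-data rule.

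**Expected loss.** Section 9.1 enrols 24 per arm "to allow for up to 20% discontinuation or loss-to-follow-up".

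**Samples from people who stop.** Section 6.1 lists safety laboratory tests, fasting lipids and banked samples at early discontinuation. Sections 6.2 and 8.3 tie that visit to at least 12 weeks on study drug. Section 6.4 keeps participants who stop for an adverse event on study, but also takes participants off study after 14 or more days off drug.

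**The concern.** A two-sample rank test of a Week 48 value can use only people who have one. It also ignores what was already known about each person from baseline and Week 24. Two things follow.

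- **Precision.** In a trial of about 20 completers per arm, an unadjusted comparison leaves the variance explained by the baseline value in the error term.
- **Bias.** The completers' comparison is safe if loss is unrelated to outcome, or related to it in the same way in both arms. The protocol gives a route to a difference. It is open label. Section 7.0 mandates drug interruption for toxicity in Arm A only, while Arm B is managed by standard practice with the aim of continuing therapy. Section 8.3 withholds study treatment for most Grade 3-4 laboratory abnormalities, and a long enough interruption ends participation under 6.4. Lipids and bilirubin are carved out of the withholding rule, but glucose, transaminases and creatinine are not, and tolerability can drive loss in either arm.

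**Working it through.** **1. The plan's own figure.** Section 9.1 states that "20 TW per arm provides 90% power to detect a minimum between-group CAP difference of 56 dB/m", with SD 53. A two-sided 5% t-test at 20 per arm has 90.2% power for 56/53 = 1.057 SD and a detectable difference of 55.8 dB/m, so the figure reproduces. On attrition, 24 × 0.8 = 19.2 completers per arm, and 20/0.8 = 25 would be needed to keep 20. This is a small difference and not the point here. At 19.2 per arm the SE of an unadjusted contrast is √(2/19.2) = 0.32 SD, and the detectable difference at 90% power is 1.075 SD.

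**2. Assumptions.** The documents give no between-visit correlation ρ, so I take 0.5-0.8. I lose 5 of 24 per arm after Week 24 (21%), with no true effect. In one arm, loss follows a score equal to the standardised Week 24 value plus standard normal noise; in the other it is random.

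**3. Bias of the completers' contrast.** The kept fraction is 19/24 = 0.792, with normal quantile 0.812 and density there 0.287. The mean shift of the standardised score among those kept is 0.287/0.792 = 0.362. The Week 24 value correlates 1/√2 with the score, so its shift is 0.362/√2 = 0.256 SD, and the Week 48 shift is 0.256ρ.

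| Pattern of loss | ρ = 0.5 | ρ = 0.7 | ρ = 0.8 |
|---|---|---|---|
| One arm, formula | 0.13 | 0.18 | 0.20 |
| One arm, simulated (20,000 trials) | 0.12 | 0.17 | 0.20 |
| Rank-sum type I error, one arm | 6.9% | 8.3% | 9.6% |
| Opposite patterns, simulated bias | 0.25 | 0.35 | 0.40 |
| Same pattern in both arms, simulated bias | 0.00 | 0.00 | 0.00 |

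With Week 24 in a regression/likelihood estimate, the simulated bias is at most 0.006 SD throughout. A separate simulation of one-arm loss gave completer bias of 0.09-0.16 SD, so 0.1-0.2 SD is a fair summary.

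**4. What baseline alone would do.** Adjusting completers for baseline leaves a bias of 0.256 × (ρ − ρ²) if all pairs of visits correlate equally: 0.06, 0.05 and 0.04 SD. If correlation decays with time (ρ between adjacent visits, ρ² from Week 0 to 48), it leaves 0.256 × (ρ − ρ³): 0.10, 0.09 and 0.07 SD. The separate simulation gave 0.03-0.08 SD. Baseline adjustment removes part of the bias; Week 24 removes the rest under this mechanism.

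**5. Precision.** Let m = 0.2 be the fraction lost after Week 24.

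- Baseline adjustment cuts variance by ρ² under equal correlations: 25% to 64%. Under decay it is ρ⁴: 6% to 41%.
- Week 24, beyond baseline, cuts it by m × (partial correlation)². Under equal correlations this is 0.2 × [ρ/(1+ρ)]² = 2.2% to 4.0%. Under decay it is 0.2 × ρ²/(1+ρ²) = 4.0% to 7.8%.

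**The case against.** Several points on the other side stand.

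- **Section 9.6 names no visit.** A reader might infer that it restricts testing to Week 48. It does not; that reading comes from the objectives. Its mention of within-group comparison may hint at change over time, but no pair of visits is defined and nothing brings Week 24 into the between-arm comparison.
- **Not everyone who leaves after Week 24 is lost.** A reader might infer that they contribute nothing. The discontinuation visit collects the same fasting samples, and 6.4 provides for follow-up after stopping for an adverse event. What is missing is a rule for using those values, and people who simply stop attending give none.
- **Most Week 24 results are unknown when decisions are made.** Insulin, oxidized LDL and the biomarkers are batched, so loss can depend on them only indirectly. Lipids and glucose are reported in real time, but asymptomatic high cholesterol or triglycerides need not stop treatment (7.2, 7.3).
- **The bias scenario is favourable to the model.** Loss was made to depend only on the observed Week 24 value, and all of it was placed after Week 24. The 20% in 9.1 covers loss at any time.
- **Without baseline in the calculation, Week 24 appears to be worth more.** The reduction would be 0.2 × ρ² = 5-13% of variance. That figure should not be used for a model that already adjusts for baseline.
- **These are secondary endpoints in a pilot, analysed as exploratory.** That excuses the lack of multiplicity adjustment. It does not remove bias.

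**Conclusion.** The gap is real but modest. For lipids, glucose, insulin/HOMA-IR and biomarkers, the plan collects baseline and Week 24 values, gives them no stated part in the main comparison, drops people without a Week 48 value, and does not say how discontinuation-visit values count.

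The size depends on assumptions outside the documents. With about 20% lost after Week 24, correlations of 0.5-0.8 and value-dependent loss in one arm, the bias is about 0.1-0.2 SD, against an SE of 0.32 SD. With the same pattern in both arms it is about zero. A reader might conclude that the Week 48 results will be biased by attrition; the documents show only that they are exposed to it if loss differs by arm in relation to outcome.

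Most of the precision gain comes from baseline adjustment. Week 24 adds 2-4% under equal correlations, up to about 8% if correlation decays; its main value is protection against arm-differential loss. CAP (the sizing endpoint), LSM and DXA have no Week 24 value and gain nothing from it. For eGFR, AST and ALT the benefit is likely to be smaller, since Weeks 4 and 12 lie far from Week 48.

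**What to change.** Add to Section 9.6, before any outcome data are compared by arm:

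1. **Model.** Analyse lipids, glucose, HOMA-IR and log biomarkers in all randomized participants with a likelihood-based repeated-measures model: baseline value, arm, visit and arm-by-visit, using Weeks 24 and 48, with unstructured covariance. The Week 48 arm contrast is the result. State that someone with no post-baseline value contributes nothing when baseline is a covariate. Objective 1.3.6 is worded as a frequency, so say that continuous HOMA-IR (listed in 9.4) is modelled and the frequency is reported alongside.
2. **Discontinuation-visit values.** State how each is assigned, for example to the nearer of Weeks 24 and 48 by sample date, and whether values taken after stopping the regimen count. The two follow-up rules in 6.4, and the 12-week condition in 6.2 and 8.3, must be reconciled so that it is clear who supplies such a sample.
3. **Sensitivity.** Keep the Week 48 rank-sum test. A simple shift of the unobserved Week 48 values by arm would test the missing-data assumption.
4. **Optional.** Use the same form with Weeks 4, 12 and 48 for eGFR, AST and ALT.

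The cost is wording and a little programming; every sample is already scheduled. The downside is that the model assumes values are missing at random and roughly normal after log transformation, which the retained rank-sum and shift analyses help to check.

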## **4.0 Selection and enrollment of participants**

### **4.1 Inclusion Criteria**

- 4.1.1 Self-identified TW
- 4.1.2 Age 18 or older
- 4.1.3 Confirmed HIV-1 infection
- 4.1.4 HIV-1 RNA <50 copies/mL at screening and for ≥24 weeks prior to entry. Participants with a single “blips” to HIV-1 RNA <500 copies/mL will be permitted to enroll.
- 4.1.5 Current ART with 2 NRTIs (TDF, TAF or ABC with FTC or 3TC) *and a 3rd agent*. Study participants are not required to be on their first regimen. However, patients who are not on their first ART regimen must not have previously substituted drugs secondary to known resistance to integrase inhibitors or components of their NRTI backbones. Other reasons for substitution such as medication intolerance or patient preference are acceptable. No changes in ART in the 12 weeks prior to screening.
- 4.1.6 Current female hormone therapy use.
- 4.1.7 Ability and willingness of subject to provide informed consent.

